8.3.5.2. Deaths

For any death occurring during the subject's study participation, regardless of attribution, the Investigator will report the death within 24 hours to the Sponsor's Medical Monitor and their designated safety management vendor on an SAE form.

The Investigator should notify the Sponsor and their designated safety management vendor of any death or other SAE occurring after a subject has discontinued or terminated study participation that may reasonably be related to the study.

Roxadustat Protocol FGCL-4592-096 A01

The Investigator must submit the SAE Report Form and complete the appropriate CRF page for the event that led to the subject's death.

When reporting a death, the event or condition that caused or contributed to the fatal outcome should be recorded as the primary event term on the SAE Report Form.

8.3.6. Pregnancies: Reporting and Follow-up

A pregnancy in a female subject or a male subject's female partner must be confirmed by positive serum β-HCG test(s). If pregnancy is suspected, study drug may need to be interrupted until pregnancy is ruled out. If a female subject or the female partner of a male subject becomes pregnant while the subject is receiving study treatment or within 12 weeks after the last dose of study treatment, a Pregnancy Report Form must be completed and submitted to the Sponsor (by way of its designated safety management vendor) within 24 hours of the Investigator learning of the pregnancy. A pregnant subject is immediately withdrawn from receiving study treatment. The Investigator must follow the pregnancy to completion to ascertain both its outcome and whether any AEs occur. Pregnancy itself is not an AE. However, the Investigator should report the information to the sponsor on the designated forms. Pregnancies are followed up to outcome. The outcome of the pregnancy must be reported by the Investigator on a Pregnancy Outcome Report Form, which should be sent to the Sponsor and/or its designated safety management vendor within 24 hours of the Investigator learning of the outcome.

8.3.7. Abnormal Laboratory Findings

Laboratory values will be collected throughout the study to assess for safety. The Investigator must review and assess all laboratory results in a timely manner, and determine whether the abnormal laboratory values, if any, are clinically significant or not clinically significant, and whether there are associated signs and symptoms. Clinically significant laboratory abnormalities will be reported as AEs.

An abnormal laboratory finding in absence of any other signs or symptoms is not necessarily an AE. If the abnormal laboratory finding is accompanied by signs or symptoms, report the signs and symptoms as the AE in lieu of the abnormal laboratory value. If a diagnosis is available, report the diagnosis.

An abnormality identified during a medical test should be defined as an AE only if the abnormality meets one of the following criteria:

- Induces clinical signs or symptoms
- Requires active intervention
- Requires interruption or discontinuation of study medication
- In the opinion of the Investigator, the abnormality is clinically meaningful and significantly different from baseline.

8.3.8. Disease Progression

Disease progression can be considered as a worsening of a subject's condition attributable to the disease for which the investigational product is being studied. It may be an increase in the severity of the disease under study and/or increases in the symptoms of the disease. As anemia is the condition being investigated in this study, worsening anemia should not be reported as an AE unless the subject is hospitalized.

Protocol FGCL-4592-096 A01

Roxadustat

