3.3. Safety Endpoints

Study-specific safety will be assessed by evaluating the following:

- Incidence of treatment emergent adverse events (TEAEs) and treatment emergent serious adverse events (TESAEs)
- Clinically significant changes in laboratory values from baseline
- Vital signs

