8. SAFETY

8.1. Background

Subjects will be asked for the occurrence of potential AEs during each study visit. In addition, all AEs reported spontaneously during the course of the study will be recorded. The Investigator must immediately (within 24 hours of becoming aware) report to the sponsor all SAEs, regardless of whether the Investigator believes they are related to the study drug.

The definitions of an AE, suspected adverse reaction, adverse reaction, and SAE are described below in accordance with the FDA Final Rule Vol 75, No 188, September 29, 2010; Article 18 of Directive 2001/20/EC of the European Parliament and of the Council of 4 April 2001and the ICH E2A guidance.

8.2. **Definitions**

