8.2.1. Definition of an Adverse Event

An AE is any untoward medical occurrence associated with the use of a drug in humans, whether or not considered drug-related.

An AE can be any unfavorable and unintended sign (e. g., an abnormal and clinically significant laboratory finding), symptom, or disease temporally associated with the use of a drug, without any judgment about causality. This includes any occurrence that is new in onset or aggravated in severity or frequency from the BL condition, or abnormal results of diagnostic procedures, including laboratory test abnormalities. An AE can arise from any use of the drug (e.g., off-label use, use in combination with another drug) and from any route of administration, formulation, or dose, including an overdose.

An AE includes medical conditions, signs, and symptoms not previously observed in the subject that emerge during the protocol-specified AE reporting period, including signs or symptoms associated with an underlying condition that were not present prior to the AE reporting period (Section 8.3.1)

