8.2.2. Definition of a Serious Adverse Event

An **SAE** is any AE or suspected adverse reaction that results in any of the following outcomes:

- Death
- A life-threatening AE (i.e., if in the view of the Investigator or sponsor, the subject was at immediate risk of death at the time of the event). Life-threatening does not refer to an event which hypothetically might have caused death if it were more severe.
- Inpatient hospitalization or prolongation of existing hospitalization
- A persistent or significant incapacity or substantial disruption of the ability to conduct normal life functions
- A congenital anomaly or birth defect
- A medically important event not meeting the above criteria, but which may jeopardize a patient or may require medical or surgical intervention to prevent one of the other criteria listed in this definition. Examples of such medical events include allergic bronchospasm

requiring intensive treatment in an emergency room or at home, and blood dyscrasias or convulsions that do not result in inpatient hospitalization

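### Protocol 8.3.8 makes hospitalization the only ground for reporting worsening anemia, so other non-fatal serious worsening has no reporting route

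*Protocol*

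**What the plan says.** Protocol 8.3.8 (Disease Progression) describes progression as worsening attributable to the disease under study. It notes that anemia is that condition and concludes that "worsening anemia should not be reported as an AE unless the subject is hospitalized". Admission is the only exception it names.

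The other safety sections are broader:

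- **8.2.1 (AE definition):** "This includes any occurrence that is new in onset or aggravated in severity or frequency from the BL condition". Anemia is not excepted.
- **8.2.2 (SAE definition):** an SAE "is any AE or suspected adverse reaction that results in any of the following outcomes". Six outcomes follow, among them events where "the subject was at immediate risk of death at the time of the event" and, as a separate item, "Inpatient hospitalization or prolongation of existing hospitalization". The examples of medically important events include "blood dyscrasias or convulsions that do not result in inpatient hospitalization".
- **8.1:** the investigator must, within 24 hours of becoming aware, "report to the sponsor all SAEs, regardless of whether the Investigator believes they are related to the study drug".
- **8.3.2:** recurrence or worsening of a medical condition is recorded as an AE.
- **8.3.7:** clinically significant laboratory abnormalities are reported as AEs. One listed criterion is that the abnormality needs active intervention.
- **8.3.5.2:** every death during participation goes on an SAE form within 24 hours, whatever the attribution.

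Protocol 3.3 makes the incidence of TEAEs and TESAEs a safety endpoint. SAP 10.1.1 builds those tables from AEs. It counts a pre-existing condition that became more severe on treatment, and it has no rule for anemia.

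**The concern.** The primary objective (Protocol 3.1.1) is to confirm that the dosing regimens are safe as well as effective. Subjects who convert stop their ESA and start roxadustat at a dose taken from a table. A marked fall in Hb afterwards is one of the ways in which a starting dose or titration rule could fail a subject. If such a fall meets a seriousness criterion but is managed without admission, 8.3.8 tells the site not to record even an AE. The sponsor then receives no 24-hour SAE form, and the event is absent from the safety tables.

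There is also a consistency problem. A site that follows 8.3.8 and a site that follows 8.1 and 8.3.2 would handle the same event differently. TEAE and TESAE incidence would then depend partly on which section each site applied.

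**Working it through.** The plan states no figure on this point, so the check compares the text of the sections.

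**Step 1. Which seriousness outcomes still have a reporting route when worsening anemia is managed without admission?**

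| Outcome in 8.2.2 | Route |
|---|---|
| Death | Kept by 8.3.5.2 |
| Life-threatening | None under 8.3.8 |
| Hospitalization or its prolongation | Kept by 8.3.8 |
| Persistent or significant incapacity | None under 8.3.8 |
| Congenital anomaly or birth defect | Not applicable to worsening anemia |
| Medically important event | None under 8.3.8 |

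Of the six outcomes, two keep a route and one does not apply: 6 − 2 − 1 = 3 outcomes without a route.

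**Step 2. How does the loss arise?** 8.2.2 defines an SAE as an AE or suspected adverse reaction with a listed outcome. 8.3.8 acts earlier: it tells the site not to report the event as an AE, so seriousness may never be assessed. The most literal conflict is therefore with the sections that decide what counts as an AE, namely 8.2.1, 8.3.2 and 8.3.7. The conflict with 8.2.2 and 8.1 follows from it.

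**Step 3. Does the SAP recover these events?** No.

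- SAP 10.1.1 has no step that derives an anemia event from Hb, transfusion or rescue data.
- SAP Appendix 3 lists no Hb limit among its potentially clinically significant laboratory ranges.
- SAP 5.1 puts local laboratory values in listings only, so a low Hb measured only locally would not be summarized.

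**Step 4. What is still captured elsewhere?**

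- Protocol 4.7.3 records rescue therapy and its reason in the eCRF, and 4.7.3.2 records all ESA use.
- SAP 9.2.1 analyzes time to first RBC transfusion from the first dose.
- SAP 9.2.8 reports the proportions with transfusion and with rescue, but only from Day 29.
- SAP 10.2 summarizes central Hb as a safety laboratory parameter.

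These data show that Hb fell or that treatment was given. None carries a seriousness classification or an assessment of relationship to study drug, and none triggers the 24-hour SAE form.

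**Step 5. Size.** The documents give neither a rate of severe anemia, nor a share managed without admission, nor a share meeting 8.2.2. All three would be needed. Only the scale per subject can be stated: with about 300 subjects in the safety set, each subject whose only TESAE is omitted lowers the overall TESAE proportion by 1/300 = 0.33 percentage points.

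**The case against.** The strongest defense is that leaving progression of the studied disease out of AE reporting is a legitimate design choice, and that a specific rule such as 8.3.8 limits a general one such as 8.2.1. The first part stands: exempting non-serious worsening is acceptable. The second part explains how the events drop out but does not restore them. 8.1 has no exception for anemia, and nothing in 8.3.8 says why admission should be the only outcome that matters.

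A second defense is scope. 8.3.8 describes progression as worsening due to the disease, so anemia from bleeding, or arguably from a poor conversion dose, falls outside it. That is a fair reading of the first sentence of 8.3.8. Its operative sentence, however, refers to worsening anemia without any qualifier on cause, and a site cannot be expected to infer one.

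Several stronger conclusions might be drawn, and the documents do not support them:

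- **That all serious anemia events without admission disappear.** Deaths are reported, and Hb, transfusion and rescue data are kept. The fault lies in safety classification and SAE reporting.
- **That a transfusion given without admission is in itself a serious event.** 8.2.2 requires immediate risk of death in the investigator's or sponsor's view, significant incapacity, or medical importance. A transfusion does not automatically meet any of these.
- **That the blood-dyscrasia example settles the matter.** Whether worsening anemia of CKD is a blood dyscrasia is arguable. The example shows only that an event can be serious without admission.
- **That reports to health authorities are materially depleted.** Under 8.3.4 a typical presentation of the underlying disease is rated not related, and the sponsor's duty described there concerns adverse reactions and suspected adverse reactions. What is clearly at risk is the SAE form to the sponsor.

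**Conclusion.** The point holds for non-fatal worsening anemia that meets the life-threatening, incapacity or medically important criterion and is managed without admission. As written, 8.3.8 gives such events no reporting route, against 8.1 and 8.2.2, and it is inconsistent with 8.2.1, 8.3.2 and 8.3.7. The consequences are missing 24-hour SAE reports to the sponsor and a downward bias in TEAE and TESAE incidence wherever sites follow 8.3.8.

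The size of that bias is unknown. A reader might want to put a number of subjects on it, but any such number would need rates that the documents do not give. It would also have to treat every severe episode as serious, although 8.3.2 lists severity and seriousness as separate attributes. The conclusion rests on the wording alone and assumes only that some sites will apply 8.3.8 literally. The study is single-arm and descriptive, so no hypothesis test is affected. The change is still worth making because safe dosing is part of the primary objective and the correction is small.

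**What to change.** 1. In Protocol 8.3.8, replace the hospitalization exception with: *unless it meets any seriousness criterion in Section 8.2.2*.
2. In 8.2.1, 8.3.2 and 8.3.7, add a cross-reference to 8.3.8 stating that non-serious worsening anemia is exempt. Without this, the conflict over non-serious events would survive the first edit.
3. In SAP 10.1.1, state how worsening anemia is counted in the TEAE and TESAE tables.

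The cost is one changed sentence, three cross-references, a short SAP statement and a notice to sites. In operation it means a few more SAE forms and possibly a slightly higher TESAE rate. No dosing, rescue or treatment rule changes.

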9. STATISTICAL CONSIDERATIONS

Descriptive summaries will be presented for study parameters including baseline characteristics, safety, and efficacy.

Continuous variables will be reported in mean, standard deviation or standard error, median, minimum, and maximum.

Categorical variables will be reported by the frequency and percentage of subjects within each outcome category.

Analyses of the efficacy data will be based on the Full Analysis Set (FAS) Population.

Safety data will be summarized descriptively based on the Safety Population.

Operational characteristics of the drug will be evaluated qualitatively and descriptively.

9.1. Sample Size Determination

Approximately 300 subjects with anemia of CKD (either with or without prior treatment with an ESA before enrolment) and on hemodialysis are planned in this study. This number of subjects distributed across the specified number of sites is adequate to evaluate the primary study objective.

Assuming the proportion of subjects that maintain Hb levels ≥ 10 g/dL from Weeks 16 to 24 is at least 80%, with a sample size of 300, the study will be able to produce a 95% confidence interval (CI) with a width equal of 9.5%.

9.2. Analysis Sets

The FAS set will consist of all subjects who signed informed consent, who were enrolled, and who provided baseline Hb data and data for at least one post baseline Hb time point. The FAS set will be used for all efficacy endpoints.

The Safety analysis set will include all enrolled subjects receiving at least 1 dose of study treatment. The safety analysis set will be used for all safety endpoints and exposure to study treatment outcomes.

9.3. Analysis of the Efficacy Endpoints

The efficacy endpoint will be evaluated using the proportion (%) of subjects with mean value of Hb measurements of Week 16-Week $24 \ge 10$ g/dL.

The 95% CI of the response rate will be presented based on the exact method of Clopper-Pearson.

For efficacy analysis, a multiple imputation (MI) method will be used. This will be implemented on the raw Hb values, then the Hb-relates endpoint summaries will be derived based on the imputed data (algorithm as used for the previous phase 3 studies).

For continuous endpoints, changes from baseline will be presented descriptively. Missing Hb values will be imputed using a multiple imputation procedure.

Proportion of responders will be presented descriptively with count and percentages and 95% confidence interval of the responder rate.

Time to response will be analyzed using the Kaplan-Meier method with KM curve plotted.

Protocol FGCL-4592-096 A01

9.4. Safety Analyses

Roxadustat

The Safety analyses will be performed using the Safety Analysis Set (SAF). Safety parameters include AEs, SAEs, laboratory parameters and vital signs.

The number and percentage of subjects reporting treatment-emergent AEs (TEAEs) and TESAEs will be tabulated.

Descriptive statistics will be presented for laboratory and vital signs.

10. DIRECT ACCESS TO SOURCE DOCUMENTS

Following site prequalification and/or initiation of the study site, periodic monitoring visits and site closeout visits will be made by Sponsor or its designee. The investigator must provide direct access to, and allocate sufficient space and time for, the monitor to inspect subject source records, eCRFs, queries, collection of local laboratory normal ranges (if applicable), investigational product accountability records, and regulatory documents in accordance with GCP and ICH E6 guideline. The purpose of study monitoring is to verify the following:

- The rights and well-being of human subjects are protected
- The reported data are accurate, complete, and verifiable from source documents
- All data are collected, tracked, and submitted by the site to Sponsor or designee, including unscheduled and missed assessments
- The reported data are reconciled across all data sources (e.g., laboratory, safety, IWRS, clinical databases)
- The conduct of the study is in compliance with the currently approved protocol/amendment(s), with GCP, and with the applicable regulatory requirement(s)

The investigator must also permit the FDA or other applicable regulatory authorities to inspect facilities and records pertaining to this study if so requested. If the investigator is notified of an inspection pertaining to this study by the FDA or other applicable regulatory authorities, the investigator must notify Sponsor immediately.

11. QUALITY CONTROL AND QUALITY ASSURANCE

11.1. Data Quality Assurance

Quality assurance and quality control systems will be implemented and maintained with Standard Operating Procedures by FibroGen and its designee(s), as appropriate, to ensure that this clinical study is conducted and data are generated, documented (recorded) and reported in compliance with the protocol, ICH E6 (GCP), and other applicable regulations.

This study will be monitored by FibroGen or designee in accordance with GCP, and may be audited or reviewed by an independent Quality Assurance department, IRB/IEC, and/or regulatory authorities. This implies that monitors and auditors/inspectors will have the right to inspect the study sites at any time during and/or after completion of the study and will have direct access to data/source documents, including the subject's file. By participating in this study, Investigators agree to this requirement.

The purpose of trial monitoring is to verify the following:

- The rights and well-being of human subjects are protected.
- The reported data are accurate, complete, and verifiable from source documents.
- All data are collected, tracked, and submitted by the site to FibroGen or designee, including unscheduled and missed assessments
- The reported data are reconciled across all data sources (e.g., laboratory, safety, IRT, clinical databases).
- The conduct of the trial is in compliance with the currently approved protocol/amendment(s), with GCP, and with the applicable regulatory requirement(s).

Measures will be undertaken to protect the confidentiality of records that could identify subjects, respecting the privacy and confidentiality rules in accordance with applicable regulatory requirements.

11.2. Audit and Inspection

Authorized representatives of the sponsor, a regulatory authority, an independent ethics committee (IEC) or an institutional review board (IRB) may visit the investigator site to perform audits or inspections, including source data verification. The Investigator will allow the sponsor auditor, regulatory authority or ethics committee representative to inspect the drug storage area, study drug stocks, drug accountability records, subject charts and study source documents, and other records relative to study conduct. The purpose of an audit or inspection is to systematically and independently examine all study-related activities and documents to determine whether these activities were conducted, and data were recorded, analyzed, and accurately reported according to the protocol, GCP guidelines of the International Conference on Harmonization, and any applicable regulatory requirements. The investigator should contact the sponsor immediately if contacted by a regulatory agency about an inspection.

12. ETHICS

12.1. Ethical Considerations

The study will be conducted in accordance with FDA regulations, ICH E6 Guideline for GCP, the Declaration of Helsinki, any other applicable regulatory requirements, and IRB or independent ethics committee (IEC) requirements.

12.2. Communication with the Institutional Review Board or Independent Ethics Committee

This protocol, the Informed Consent Form, the IB, and any information to be given to the subject must be submitted to a properly constituted IRB/IEC by the Investigator for review and approved by the IRB/IEC before the study is initiated and before any investigational product is shipped to the Investigator. In addition, any subject recruitment materials must be approved by the IRB/IEC before the material is used for subject recruitment.

The investigator is responsible for obtaining reapproval by the IRB/IEC annually or more frequently in accordance with the regulatory requirements and policies and procedures established by the IRB/IEC. Copies of the investigator's annual report and other required report to the IRB/IEC and copies of the IRB/IEC continuance of approval must be furnished to FibroGen. A copy of the signed form FDA 1572 must also accompany the above approval letter provided to FibroGen. Investigators are also responsible for promptly informing the IRB/IEC of any protocol changes or amendments, changes to the Investigator's Brochure, and other safety-related communications from FibroGen. Written documentation of IRB approval must be received before the amendment is implemented.

Investigators must also enter the names of the staff that are involved in the study on the Delegation of the Authority form and sign the form (including their responsibilities). This form must be updated when responsibilities of the staff change.

